13.3 Determining adverse event causality

The Investigator will assess and classify the relationship of an AE to the trial IMP (ThermoDox®) as follows:

Classification	Relationship	Definition
Drug-related	Definitely related	
 Starts within a time related to the study drug administration and No obvious alternative medical explanation.
	Probably related	
 Starts within a time related to the study drug administration and Cannot be reasonably explained by known characteristics of the patient's clinical state.
	Possibly related	
 Starts within a time related to the study drug administration and A causal relationship between the study drug and the adverse event is at least a reasonable possibility.
Not drug related	Probably related not	
 The time association or the patient's clinical state is such that the study drug is not likely to have had an association with the observed effect.
	Definitely related not	
 The AE is definitely not associated with the study drug administered.

The Investigator must endeavour to obtain sufficient information to confirm the causality of the adverse event (i.e. relation to the study drug, focused ultrasound exposure, liver biopsy, other illness, progressive malignancy or other cause) and give their opinion of the causal relationship between each AE and study drug, FUS and/or biopsy procedure. This may require instituting supplementary investigations of significant AEs based on their clinical judgement of the likely causative factors and/or include seeking a further specialist opinion.

13.4 Expected adverse events

Appendix 2 of the current approved ThermoDox[®] IB [44] lists all the adverse events associated with the use of ThermoDox[®] in clinical studies. ThermoDox[®] contains Adriamycin[®] (doxorubicin) as its active chemotherapy agent and ThermoDox[®] has a similar toxicity profile to doxorubicin. Appendix 1 of the current approved ThermoDox[®] IB [44] lists all the adverse events known to be associated with the use of doxorubicin. A copy of this document must be held in the Site File for reference.

Please note much of the adverse event data for ThermoDox[®] has been obtained from a global, randomized Phase III study (HEAT) which involves combining ThermoDox[®] with RFA in the treatment of hepatic tumours, in patients with inoperable hepatocellular carcinoma (HCC). Adding 50mg/m² of ThermoDox[®] to RFA was found to be safe with an adverse event profile similar to that of the single agent doxorubicin. However given the difference in patient population, it is possible that in this study population other side effects may occur, or the patient might suffer a more severe reaction.

As per ThermoDox[®] IB amendment version date 11th October 2013 (the current approved ThermoDox[®] IB at the time of the initial trial approval), grade 3+ neutropenia and leucopenia were the only¹⁹ SAEs occurring in over 5% of HEAT Study patients and were not seen in the arm receiving RFA without ThermoDox[®] (Table 7). The detailed and current list of SAEs and AEs in 701 patients for this study, can be found in Appendix 2 of the current approved ThermoDox[®] IB

¹⁹ The only other grade 3+ adverse events affecting at least 5% of subjects were elevations in liver enzymes which is an expected occurrence in the patient group used for the HEAT study (hepatocellular carcinoma). The RFA alone vs RFA+ThermoDox[®] study arms did not differ significantly in this respect.

[44]. Further details regarding the frequency of AEs and SAEs in patients treated with ThermoDox® using targeted application of heat by RFA or microwave have been included in a recent publication [10].

Adverse Event	RFA Alone N=347		RFA+ThermoDox® N=354		p-value
	N	%	N	%	
Neutropenia	0	0	65	18.9	<0.0001
Leukopenia	0	0.0	21	6.1	<0.0001

Table 7: SAEs affecting at least 5% of patients enrolled in the Phase III, randomized, double-blinded, dummy-controlled study of the efficacy and safety of ThermoDox® in combination with RFA compared to RFA-alone in the treatment of non-resectable HCC. Data obtained from the ThermoDox® Investigator's Brochure (Amendment Version October 11, 2013).

This study involves the use of FUS to induce mild hyperthermia. A recent study performed at Oxford involving 30 patients in four trial protocols has shown *ablative* FUS or high-intensity FUS (HIFU) to be both safe and feasible for the treatment of liver and kidney tumours [45]. Adverse events are summarised in Table 8. It should be noted that thresholds of acoustic power required for mild hyperthermia, as required this study, are envisaged to be well below those required for ablative HIFU and thermal cell death.

Event	CTC grade			
	0	1	2	3
Discomfort at treatment site	6	16	7	1
Skin toxicity at treatment site	22	7	1	0
Oedema at treatment site	22	3	3	2
Fever	26	3	1	0
Other	27	3	0	0

HIFU = high-intensity focused ultrasound; CTC = common toxicity criteria. ^aNumber of patients who experienced each adverse event by grade.

Table 8: Adverse events possibly or probably related to HIFU treatment^a. Reproduced from Illing et al., 2005 [45].

Evidence for the primary endpoint for this study requires laboratory analysis of tumour tissue obtained by image guided liver biopsy through a co-axial biopsy needle as per current guidelines. The complications of performing image guided liver biopsy using guidelines have been reviewed following a recent UK-wide audit [48] and are summarised in Table 9. Out of 3496 cases, 376 patients had minor complication alone, 22 patients had at least one major complication and there were 4 deaths, all attributable to post-biopsy haemorrhage.

A: Minor Complications								
Response	Minor Pain	Severe Pain	Hypotension					
Yes	338 (9.94)	36 (1.06)	26 (0.75)					
No	3062 (90.06)	3365 (98.94)	3426 (99.25)					
Total	3400	3401	3452					
B: Major Complications								
Response	Hemorrhage	Hemobilia	Punctured Kidney	Punctured Bowel	Punctured Gallbladder	Punctured Lung	Puncture of Other Organ	Death
Yes	14 (0.40)	2 (0.06)	1 (0.03)	1 (0.03)	0 (0.00)	1 (0.03)	0 (0.00)	4 (0.11)
No	3462 (99.60)	3453 (99.94)	3457 (99.9)	3457 (99.97)	3455 (100.00)	3454 (99.97)	3471 (100.00)	3482 (99.89)
Total	3476	3455	3458	3458	3455	3455	3471	3486
C: Postbiopsy Procedure								
Response	Blood Transfusion	Percutaneous Drainage	Laparotomy	Embolization				
Yes	12 (0.34)	4 (0.12)	1 (0.03)	2 (0.06)				
No	3470 (99.66)	3464 (99.88)	3467 (99.97)	3469 (99.94)				
Total	3482	3468	3468	3471				

Table 9: Post- liver biopsy complications, mortality and subsequent treatment and interventions. Data is represented as numbers of cases. Numbers in parentheses are percentages. Reproduced from Howlett et al., 2013 [48].

13.5 Suspected Unexpected Serious Adverse Drug Reactions (SUSARs)

All SUSARs must be reported to the responsible Authority and main REC within 7 or 15 days, depending on the seriousness criteria, by the Sponsor or their delegate within the required timelines. The Sponsor or their delegate will ensure that all SUSARs are also reported to the MHRA. It is therefore important that the SAE form is faxed as detailed below as soon as, and no later than, 24 hours after the site are aware of an SAE or significant updated information. In addition, other safety issues qualify for expedited reporting where they might materially alter the current risk assessment of an IMP or be sufficient to change IMP administration or the overall conduct of the trial. Responsibility for expedited safety reporting will be assigned by the Sponsor.

The TARDOX trial office shall notify Celsion of all SUSAR's within one working day of becoming aware of them.

13.6 Expedited reporting of SAEs

The following SAE reporting requirements apply regardless of the Investigator's assessment of the causality or expectedness of the SAE (see section 13.10 for exceptions). All SAEs should be reported on the trial SAE report form (see SAE report form and instructions for completion). Please note that the SAE report form is a paper form and these data cannot be entered into the eCRF system (OpenClinica).

SAE forms must be completed and faxed to the trial office on:

TARDOX Trial Office SAE [contact]

Or emailed (email preferred) to:

TARDOX Trial Office SAE Email: [contact]

SAE forms must be completed with all critical elements as soon as possible and submitted within 24 hours of becoming aware of the event all the vital elements being completed. If the SAE has not been reported within the specified timeframe, a reason for lateness must be provided when sending the SAE Report Form.

Investigators should also adhere to their local Trust policy for incident and SAE reporting in research.

The TARDOX trial office shall notify Celsion with a line listing report of all Serious Adverse Reactions (SARs) on a monthly basis.

13.7 Follow-up of Serious Adverse Events

If new or amended information on a reported SAE becomes available, the Investigator should report this on a new SAE form or update the existing form, without obscuring any initial information. All new data must be initialled and dated so that all changes are clearly identified.

Follow up will continue until all the necessary safety data for the event has been gathered. Any SAE that is on-going when a subject completes his/her participation in the trial must be followed until any of the following occurs:

- The event resolves or stabilizes;
- The event returns to baseline condition or value (if a baseline value is available);
- The event is attributed to other agent(s) or to factors unrelated to study conduct.

SAEs that are considered to be definitely unrelated to the trial intervention will be followed up as per related SAEs.

13.8 Adverse events that should be notified to trial office

AEs that are serious must be reported to trial office up to and including 30 days after the intervention date. Any SAE that occurs at any time after completion of ThermoDox® treatment or after the designated follow-up period that the investigator considers to be related to the study drug must be reported

13.9 Reporting Adverse Events on the CRF

All AEs, including Serious AEs must be recorded on the case report forms (CRF) for that patient. The information provided will include date of onset, event diagnosis (if known) or sign/symptom, severity, time course, duration and outcome and relationship of the AE to study drug. Any concomitant medications or other any therapy used to treat the event must be listed. The Investigator will provide an "other" cause for serious AEs considered to be unrelated to the study drug. The study site should ensure data entered into the CRF is consistent with the SAE report information where applicable. SAE forms should be sent to the trials office within 24 hours of the incident occurring.

Each separate AE episode must be recorded. For example, if an AE resolves completely or resolves to baseline and then recurs or worsens again, this must be recorded as a separate AE. For AEs to be considered intermittent, the events must be of similar nature and severity.

Serious Events reporting requirements

Subjects having adverse events will be monitored with relevant clinical assessments and laboratory tests as determined by the Investigator. All adverse events must be followed to satisfactory resolution or stabilization of the event(s) including the investigation for the likely causative factor. Any actions taken and follow-up results must be recorded in the subject's source documentation. Follow-up laboratory results should be filed with the subject's source documentation. For all adverse events which require the subject to be discontinued from the study, relevant clinical assessments and laboratory tests will be repeated, on at least a weekly basis, until final resolution or stabilisation of the event(s). All SAEs will be included in analysis and must be reported to Celsion, regardless of cause, and will be classified as per section 13.3.

Non Serious Events reporting requirements

All Adverse Events (AE) including Adverse Drug Reactions (ADR) occurring up to 30 days following the intervention must be recorded on the CRF. The investigator will decide if those events are related to the medicinal product (i.e. unrelated, unlikely, possible, probable, definitely and not assessable) and the decision will be recorded on the CRF. AE definitely not drug related (i.e. reported as unrelated) will not be considered as adverse drug reactions in toxicity analyses, but reported separately.

Terms and Grading of Events

MedDRA dictionary should be used to code SAES

The NCI CTCAE Version 4.0 (currently up to Version 4.03) should be used to grade AEs and where possible use the Lowest Level Terms provided. Where indicated on the form, provide the severity grade for each AE, and the worst grade recorded.

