To assess the safety of FUS-induced mild hyperthermia for drug delivery	1. Persistence of cell viability stain or percentage of cell or tissue necrosis under 30% following FUS exposure, as assessed by cytological or histological	1. Cytological or histological analysis of biopsy samples processed within 96hr of intervention†

	methods ¹⁶ ‡,§ 2. Adverse events deemed related to FUS up to 30 days post-intervention	2. Adverse event recording for 30 days post-intervention
To assess the local and systemic cytotoxic effects of ThermoDox® in this setting	1. Significant bone marrow suppression, deranged liver function and liver toxicity 2. Adverse events deemed related to ThermoDox® up to 30 days post-intervention	1. Grade 3 and 4 laboratory results from blood tests at Day 1 and Day 15 post intervention 2. Adverse event recording for 30 days post-intervention

Table 2: Secondary Objectives and Endpoints for Parts I & II of the TARDOX Study

Regarding participants for which doxorubicin has been released by optimal FUS exposure parameters:

Tertiary (Exploratory) Objectives	Tertiary (Exploratory) Endpoints	How and when data is captured
1. To establish the validity of other minimally-invasive and non-invasive methods of evaluating intratumoural uptake of doxorubicin as an alternative to that used in primary endpoint	Combined analysis of relevant end points to establish most effective alternative analytical method(s) for quantifying drug release	See below
a. Fluorescence microscopy of biopsy	Released biopsy samples exhibiting regions of nuclear or background fluorescence levels at least twice that of a suitable control, as assessed by fluorescence microscopy ‡,§	Microscopic analysis of biopsy samples processed within 96hr of intervention†
b. MR-Spectroscopy	Liver MRI/MR-Spectroscopy indicating ¹⁷ targeted delivery of doxorubicin to the tumour by demonstrating a statistically significant increase in the tumour:background ratio of signal intensity following intervention compared to baseline	MRI/MR-Spectroscopy signal within 36 hours of intervention
c. Plasma pharmacokinetics	A statistically significant decrease in total doxorubicin plasma levels over time-matched clearance levels, following HIFU-induced release	Analytical chemistry of plasma samples processed within 12hr of intervention†

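### Sections 13.3 and 13.9 draw the line for a drug-related adverse event in different places, and the 13.9 CRF list does not secure the FUS attribution that a secondary endpoint needs

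*Protocol*

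**What the plan says.** **Section 13.3** sets out a scale: "The Investigator will assess and classify the relationship of an AE to the trial IMP (ThermoDox®) as follows". It has five levels. *Definitely*, *probably* and *possibly* related are grouped as drug-related; *probably not* and *definitely not* related are grouped as not drug related. The *probably not* level is for events where timing or clinical state means that "the study drug is not likely to have had an association with the observed effect". The section then asks for the investigator's opinion on how each event relates to the drug, the FUS and the biopsy, but gives graded levels for the drug only.

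**Section 13.9**, under non-serious events, gives another list: "The investigator will decide if those events are related to the medicinal product (i.e. unrelated, unlikely, possible, probable, definitely and not assessable". It adds a rule for the analysis: "AE definitely not drug related (i.e. reported as unrelated) will not be considered as adverse drug reactions in toxicity analyses"; these events are to be reported separately. Under serious events, the same section sends classification back to 13.3. Among the items to be entered on the CRF it names "time course, duration and outcome and relationship of the AE to study drug". It also asks for another cause, but only for serious events considered unrelated to the drug.

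**Section 13.1** defines an adverse drug reaction as requiring a causal link that is reasonably possible at the least.

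**Section 3, Table 2** has two secondary endpoints that depend on attribution: events deemed related to ThermoDox, and "Adverse events deemed related to FUS up to 30 days post-intervention". Neither names a scale or a cut-point. Section 17.1 tabulates toxicity by relatedness to trial treatment, again without naming one.

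**The concern.** The two attribution endpoints, and the toxicity tables that support them, count events judged related. Such a count needs one rule for what counts as related and a recorded judgement for each cause being counted. The protocol fixes two rules that disagree on one level of the scale, and one of them leaves open how a *not assessable* rating is treated. For FUS, it asks for the judgement in one section and omits it from the recording list in another.

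This goes beyond detail that a protocol may leave to the SAP. Section 13.9 states a cut-point for the toxicity analysis, and that cut-point does not match the protocol's own scale or its own definition of a drug reaction. A SAP can choose a cut-point, but here it would have to override a stated rule. It cannot recover a FUS rating that was never collected.

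**Working it through.** The protocol gives no figure for this point, so the check is a mapping of the two scales followed by a trace of where FUS attribution is asked for and recorded.

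**Step 1: map the levels.** Inputs are the table in section 13.3 and the list and exclusion rule in section 13.9.

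| 13.3 level | 13.3 class | 13.9 level | Excluded as a drug reaction by 13.9? |
|---|---|---|---|
| Definitely related | Drug-related | Definitely | No |
| Probably related | Drug-related | Probable | No |
| Possibly related | Drug-related | Possible | No |
| Probably not related | **Not drug related** | Unlikely | **No** |
| Definitely not related | Not drug related | Unrelated | Yes |
| (none) | **Undefined** | Not assessable | **No** |

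Under 13.3, 3 of 5 levels are drug-related. Under 13.9, 5 of 6 levels are not excluded. Five levels pair one to one. The rules disagree on *probably not/unlikely*, and *not assessable* has no counterpart in 13.3.

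**Step 2: compare with the definition of a drug reaction.** Section 13.1 sets the threshold at a reasonable possibility of causation. Section 13.3 uses the same threshold to describe *possibly related*, its lowest drug-related level. Sections 13.1 and 13.3 therefore agree, and the 13.9 exclusion rule is the one out of line.

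**Step 3: see which events meet which rule.** Section 13.9 sends serious events to 13.3 and puts the six-level list under non-serious events. Section 13.2 makes every Grade 4 laboratory abnormality a serious event. So a Grade 4 neutropenia is classified under 13.3, while a Grade 3 neutropenia that is not otherwise serious meets the 13.9 list. If both were judged unlikely to be due to ThermoDox, the first would be not drug related and the second would not be excluded as a drug reaction.

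**Step 4: trace FUS attribution.**
- Needed: section 3, Table 2, as a secondary endpoint of its own.
- Asked for: section 13.3, an ungraded opinion for each event.
- Listed for the CRF: section 13.9 names relationship to study drug. The field for another cause covers only serious events unrelated to the drug.

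The gap therefore lies mainly with non-serious events, and the protocol's own background data suggest that FUS effects are mostly mild. In Table 8 (ablative HIFU, 30 patients), discomfort at the treatment site was Grade 1 in 16, Grade 2 in 7 and Grade 3 in 1. That is 16 + 7 = 23 of 16 + 7 + 1 = 24 affected patients at Grade 1 or 2. FUS here is planned at lower power, so this is only an indication.

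**Step 5: size.** Section 16.1 allows at most 28 evaluable participants. One participant moved between related and not related changes a proportion by 1/28 = 0.036, or 3.6 percentage points. The toxicity denominator may differ, because section 17.1 counts all patients from the time of intervention while section 6.1 replaces those not evaluable for the primary endpoint. The 3.6 points is thus the step at a denominator of 28, not a prediction.

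**The case against.** There is a fair case that this is a loose sentence and little more.

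- *The conflict is inferred by negation.* Section 13.9 says that unrelated events are not drug reactions; it does not say that all others are. Section 13.1 gives a reason to leave *unlikely* events out. This stands in part: the intended reading can be guessed. But the only exclusion stated for the toxicity analysis is the *unrelated* level, and someone programming the table from 13.9 would keep the *unlikely* events.
- *Section 13.3 covers any adverse event, not only serious ones.* True. A non-serious event then falls under both sections, which does not settle which rule applies.
- *The exclusion rule concerns drug reactions in toxicity analyses, while the endpoints count events deemed related, and the SAP may define that.* Correct as far as it goes. No text ties the 13.9 rule to the endpoints, but none gives them another rule either.
- *The 13.9 list is introduced as what the information will include, so it need not be complete, and the CRF is not shown.* This stands. It limits the FUS point to a mismatch between two sections.

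Three stronger readings are tempting, and the protocol does not support them. A reader might infer that the endpoints cannot be counted; in fact five levels merge without loss, and section 17.1 says that causality will be reported. A reader might infer that the CRF records drug causality only; section 13.3 requires an opinion on FUS and biopsy for every event, and the form itself cannot be inspected. A reader might want the number of events that would change class; the protocol gives neither an expected number of events per participant nor a distribution of ratings, so any such count would rest on invented inputs.

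**Conclusion.** The point holds as an inconsistency to correct. The protocol states two cut-points for drug-relatedness that disagree on events judged unlikely to be due to ThermoDox. It leaves *not assessable* without a place in 13.3, and its 13.9 rule sits badly with its own definition of a drug reaction. The ThermoDox-related endpoint therefore has no single counting rule. The FUS-related endpoint depends on an opinion that 13.3 requires but the 13.9 CRF list does not name, which matters most for non-serious events.

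The consequence is limited. Both endpoints are descriptive; the requirement of at least 50% of evaluable participants is not attached to them, and no test or threshold depends on them. The primary endpoint is untouched. Under section 13.6, expedited reporting of serious events to the trial office does not depend on causality.

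This rests on reading the 13.9 exclusion rule literally and on the protocol alone. A CRF with separate FUS and biopsy items would close the second part in practice, though the text would still need aligning.

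**What to change.** 1. Use the five-level scale of section 13.3 for serious and non-serious events, and delete the six-level list in 13.9.
2. Replace the 13.9 exclusion rule with one definition: related means definitely, probably or possibly related. This agrees with sections 13.1 and 13.3.
3. Prespecify how a not-assessable or missing rating is handled. Counting it as related is one conservative option; the essential thing is that the rule is fixed before the analysis.
4. In the 13.9 CRF list, name separate relationship items for ThermoDox, FUS and biopsy, the three causes that 13.3 already asks about. Grading all three on the same five levels would give the FUS endpoint the same cut-point.

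The cost is a wording change in 13.9, a short addition to 13.3, and a few fields on the adverse event page if they are not already there. Ratings already recorded on the six-level list can be carried over one to one, except *not assessable*, which falls under step 3.
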